#### Follow-up Period

- For efficacy - patients will be followed up on Day 14 and Day 28. If patient is no longer hospitalized, follow-up will occur by phone-call.
- For safety - patients will be follow-up 28 days after the first treatment dose is administered. If patient is no longer hospitalized, follow-up will occur by phone-call.

Two interim analyses are planned to assess futility. The first IDMC interim analysis will take place after the first 60 participants have completed Day 10 of the study to evaluate whether the study will be stopped for futility based on change from baseline in room air SpO2. The second interim analysis will take place after 150 participants have completed Day 14 post-randomization based on event rate for the primary endpoint. The purpose of the second interim analysis will be futility as well as a potential sample size re-estimation in case the actual results differ from the original assumptions.

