### 3.3 Endpoints

#### 3.3.1 Efficacy Variables

Primary:

- Proportion of participants who progress to level >4 of modified WHO ordinal scale due to COVID-19 by Day 14

Key Secondary:

- Change in room air SpO2 from baseline over time
- Change in NEWS 2 symptom score from baseline over time
- Change from baseline on the modified WHO ordinal scale at each visit up to Day 28
- Time to improvement to at least one level lower of the modified WHO ordinal scale
- Time to progression to at least one level higher of the modified WHO ordinal scale

Additional Secondary:

- Time to hospital discharge
- Incidence of mortality by Day 28

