All the categorical variables including the primary endpoint will be summarized by treatment in terms of the number of patients providing data at the relevant time point (n), frequency counts and percentages. Binary primary endpoint: (progression to critical stage/death up to Day 14) will be analyzed by a Cochran-Mantel-Haenszel (CMH) stratified for the factors used in the stratified randomization. Treatment difference will be tested using a Cochran–Mantel–Haenszel (CMH) test stratified by 1) country and 2) participant's clinical status at Baseline. For the categorical endpoints, relative risk and its 95% CI will be presented.

Percentages will be presented to one decimal place. Percentages will not be presented for zero counts. Percentages will be calculated using n as the denominator. If sample sizes are small, the data displays will show the percentages, but any textual report will describe frequencies only.

Changes from baseline in categorical data will be summarized using shift tables where appropriate.

P-values greater than or equal to 0.001, in general, will be presented to three decimal places. P-values less than 0.001 will be presented as “<0.001”.

Confidence intervals will be presented to one more decimal place than the raw data.

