#### 4.9.1.3 Handling of Dropouts or Missing Data

Any patients that are discharged from the hospital prior to Day 14 due to improvement of clinical status and their status on Day 14 cannot be obtained, then the Last Observation Carried Forward (LOCF) approach will be used to impute missing data. Only post-treatment observations will be carried forward. No baseline observations will be carried forward. To assess the robustness of the study conclusions to the choice of imputation method, a complete-case analysis (all patients with missing data for the primary endpoint are excluded from analysis) will be performed as a sensitivity analysis.

The Per-protocol population analyses will be performed using the same imputation method as for the ITT population analyses.

If the proportion and/or pattern of missing data is found to be different to that assumed, additional sensitivity analyses may be required.

In general, imputed partial dates will not be used to derive study day, duration (e.g., duration of adverse events), or elapsed time variables. In addition, imputed dates are not used for deriving the last contact date in the time to event analyses.

Imputed dates will not be displayed in listings unless otherwise stated.

The partial date imputation will follow ADaM conventions. The ADaM approach is to populate the numeric date variables with the imputed date and add a flag variable to the dataset that indicates the level of imputation.

The flag variable can contain the values: blank, 'D', 'M', 'Y'.

blank: indicates that no imputation was done

- D='Day': indicates that the day portion of the date is imputed
- M='Month': indicates that the month and day portions of the date are imputed
- Y='Year': indicates that the entire date (year, month, and day) is imputed

Imputing partial AE and prior/concomitant medication start dates:

- a) If the year is unknown, the date will not be imputed and will be assigned a missing value.
- b) If the month is unknown, then:

1. If the year matches the first dose date, then impute to the month and day of the first dose date.
2. Otherwise, assign 'January'.

c) If the day is unknown, then:

1. If the month and year match the first dose date, then impute to the day of the first dose date.
2. Otherwise, assign '01'.

Imputing partial AE and prior/concomitant medication stop dates:

- a) If the year is unknown, the date will not be imputed and will be assigned a missing value.

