### 4.9.2 Primary Efficacy Variable

Progression to level at least one level higher than baseline of modified WHO ordinal COVID-19 scale by Day 14”

The WHO 7-point ordinal scale is as follows:

1. Not hospitalized, no limitations on activities;
2. Not hospitalized, limitation on activities;
3. Hospitalized, not requiring supplemental oxygen;
4. Hospitalized, requiring supplemental oxygen;
5. Hospitalized, on non-invasive ventilation or high-flow oxygen devices;
6. Hospitalized, on invasive mechanical ventilation or ECMO;
7. Death.

The percentage and corresponding 95% CI of patients who progress to at least one level higher from baseline on the WHO 7-point ordinal scale on Day 14 will be summarized by treatment arm and overall. The odds ratio of RESP301 + SOC versus SOC alone and 95% CI intervals and p-values will be estimated using the CMH stratified by country and number of risk factors (as randomized).

WHO 7-point ordinal scale will be assessed daily while patient is hospitalized. Daily scores and changes from baseline will be summarized. Plots of mean score (with standard error bars) by treatment group over time may be produced.

A by-patient listing of the primary efficacy data will be provided

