#### NEWS 2 scores

The NEWS is based on a simple aggregate scoring system (see Fig 2 for NEWS 2 scoring system) in which a score is allocated to physiological measurements, already recorded in routine practice, when patients present to, or are being monitored in hospital (**Error! Reference source not found.**). Six simple physiological parameters form the basis of the scoring system:

1. Respiration rate
2. Oxygen saturation
3. Systolic blood pressure
4. Pulse rate
5. Level of consciousness or new confusion\*
6. Temperature

\*The patient has new-onset confusion, disorientation and/or agitation, where previously their mental state was normal – this may be subtle. The patient may respond to questions coherently, but there is some confusion, disorientation and/or agitation. This would score 3 or 4 on the Glasgow Coma Scale (rather than the normal 5 for verbal response), and scores 3 on the NEWS system.

Standard descriptive statistics (mean, standard deviation, median, minimum, maximum) and change from baseline will be used to summarize each of these scores by treatment group and visit. NEWS scores will be assessed daily while patient is hospitalized. Plots of mean score (with standard error bars) by treatment group over time may be produced.

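### The SAP sets no WHO-scale level for discharged or dead patients on days outside the Day 14 and Day 28 contacts, so daily by-arm summaries of a key secondary endpoint cover, as written, only patients still in hospital and alive

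*SAP*

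**What the plan says.** All references are to SAP version 2.0.

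- **Endpoint.** Section 3.3.1 lists among the key secondary variables "Change from baseline on the modified WHO ordinal scale at each visit up to Day 28".
- **Collection and summary.** Section 4.9.2: "WHO 7-point ordinal scale will be assessed daily while patient is hospitalized. Daily scores and changes from baseline will be summarized". It adds: "Plots of mean score (with standard error bars) by treatment group over time may be produced".
- **Scale.** Section 4.9.2 defines seven levels. Levels 1 and 2 are both out of hospital and are separated by activity limitation; level 1 is "Not hospitalized, no limitations on activities". Levels 3 to 6 are in hospital, and level 7 is death.
- **Denominator.** Section 4.2 summarises categorical variables by the "number of patients providing data at the relevant time point (n), frequency counts and percentages".
- **Contact after discharge.** Section 3.1 (Follow-up Period) on efficacy contacts: "patients will be followed up on Day 14 and Day 28. If patient is no longer hospitalized, follow-up will occur by phone-call".
- **Missing data.** The LOCF rule in Section 4.9.1.3 is worded for patients discharged after improvement when "their status on Day 14 cannot be obtained, then the Last Observation Carried Forward (LOCF) approach will be used to impute missing data".
- **Population.** Section 4.5 places all efficacy analyses on the ITT population.

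**The concern.** Daily scoring ends when a patient leaves hospital or dies. The scale itself covers both outcomes: death is level 7, and any discharged patient is at 1 or 2. Without a rule that writes those levels into later days, each daily mean is taken over a group selected by outcome, namely patients who are alive and not yet well enough to go home.

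An arm that discharges more of its milder patients keeps a sicker remainder, so its inpatient mean rises because its patients did well. An arm that loses more of its sickest patients to death shows a lower inpatient mean because its patients did badly. Either way, the by-arm means and plots for a key secondary endpoint would no longer compare the groups as randomized. Early discharge is expected: a note to the design figure allows it before Day 10, and Section 4.4.1 tabulates it.

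**Working it through.** **Step 1: does any rule fill the gap?** The SAP gives no figure to reproduce, so the first check is to read the provisions together.

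| Situation | Rule in the SAP |
|---|---|
| Discharged, Day 14 or Day 28 | Phone contact (Section 3.1) |
| Discharged after improvement, Day 14 status unobtainable | LOCF (Section 4.9.1.3) |
| Discharged, any other day | None |
| Dead, days after death | None saying that level 7 persists |

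Stretching LOCF to the other days would not help. The last inpatient score is 3 or higher, whereas the patient is by definition at 1 or 2.

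**Step 2: what could omission do?** The distribution below is an assumption; none of it is in the documents.

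*SOC arm, Day 10:* 40% discharged (half level 1, half level 2), 5% dead, and 55% in hospital split 35/40/15/10% over levels 3/4/5/6. The proportions at levels 1 to 7 are then 0.20, 0.20, 0.1925, 0.22, 0.0825, 0.055 and 0.05.

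- Mean over all patients = sum of level × proportion = 0.20 + 0.40 + 0.5775 + 0.88 + 0.4125 + 0.33 + 0.35 = 3.15.
- Mean over inpatients = (0.5775 + 0.88 + 0.4125 + 0.33) / 0.55 = 2.20 / 0.55 = 4.00.

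*RESP301 arm, 20 points more discharges.* These come from level 3 until 90% of it is used (0.17325), then from level 4 (0.02675). The proportions become 0.30, 0.30, 0.01925, 0.19325, 0.0825, 0.055 and 0.05.

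- All patients: 0.30 + 0.60 + 0.05775 + 0.773 + 0.4125 + 0.33 + 0.35 = 2.823. Difference from SOC: 2.823 − 3.15 = −0.33.
- Inpatients: 1.57325 / 0.35 = 4.495. Difference from SOC: 4.495 − 4.00 = +0.50.
- With 200 and 100 patients (300 randomized 2:1), that day's summary would rest on 0.35 × 200 = 70 and 0.55 × 100 = 55 patients.

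The range, by the same method (RESP301+SOC minus SOC; negative favours RESP301):

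| Assumed arm difference | All patients | Inpatients only |
|---|---|---|
| None | 0 | 0 |
| 10 points more discharges on RESP301 | −0.15 | +0.22 |
| 20 points | −0.33 | +0.50 |
| 30 points | −0.58 | +0.69 |
| 3 points more deaths on SOC, from its sickest | −0.03 | +0.12 |
| 5 points | −0.05 | +0.20 |
| 8 points | −0.11 | +0.28 |

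**Step 3: is reversal inevitable?** No. The table draws extra discharges from the mildest patients and extra deaths from the sickest, which favours reversal. As a contrast, take a normal latent severity cut at −0.6, 0.1, 0.5, 1.1, 1.5 and 1.9 into levels 1 to 7, and shift the whole RESP301 arm 0.4 SD towards milder disease. Discharged are 54% versus 69%, and dead 2.9% versus 1.1% (SOC versus RESP301). All-patient means are 2.73 versus 2.18, a difference of −0.55. Inpatient means are 3.98 versus 3.83, a difference of −0.15. About 72% of the difference is lost, but the sign is kept.

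**Step 4: how much does level 1 versus level 2 matter?** In the 20-point case, half of the discharged sit at each level. Moving all of them to level 2 adds 0.20 to the SOC mean and 0.30 to the RESP301 mean: (2.823 + 0.30) − (3.15 + 0.20) = −0.23. Moving all of them to level 1 gives (2.823 − 0.30) − (3.15 − 0.20) = −0.43. The size changes and the direction does not.

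**The case against.** The strongest reply is that the SAP never says discharged or dead patients are left out. The hospital condition in Section 4.9.2 is attached to assessment, the sentence on summaries carries no such limit, and Section 4.5 uses ITT for efficacy. This stands in part. Exclusion is the natural reading, because no score would exist for those days and the categorical summaries count patients with data, but it is not stated text.

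A reader might infer that discharged patients vanish from the endpoint altogether. The documents do not support that, since Section 3.1 requires efficacy contact at Day 14 and Day 28, by phone after discharge. A reader might also infer that every omitted value is known. That holds for death; after discharge only membership of 1 or 2 is known, because a discharge date says nothing about activity limitation.

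The consequence is also bounded. Section 4.9.2 names no test for the daily scores, and the plots are optional. Section 4.2 does contain a general mixed-model/ANCOVA statement with p-values, but does not tie it to this endpoint. Numbers of observations will be shown, so shrinking groups would be visible. Mortality, time to discharge, improvement and progression each have their own analysis.

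It is tempting to extend the point to NEWS 2, for which "NEWS scores will be assessed daily while patient is hospitalized". That is not a comparable gap. NEWS 2 needs measured physiology that a phone call does not supply, and it has no defined value after discharge or death. Relabelling those tables would be a presentation preference.

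Finally, the protocol's schedule of assessments and the SAP Addendum cited in Section 4.12 are not at hand, and a scoring rule there cannot be ruled out.

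**Conclusion.** The point holds as a cheap improvement to the SAP. On days other than the Day 14 and Day 28 contacts, nothing shown assigns a level to patients who have been discharged or have died. Read as written, the daily by-arm scores, changes and mean plots then describe survivors still admitted. Where discharge or death differs between arms, this can shrink or reverse the apparent difference.

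How large the effect would be cannot be taken from the documents. Under the assumptions above, the result ranges from no distortion (no arm difference in discharge or death), through a loss of about 72% with the sign kept, to full reversal. A reader might infer that bias of a particular size, or reversal, is bound to occur; the figures show only that both shrinkage and reversal are possible. The primary endpoint and the time-to-event analyses are not affected.

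**What to change.** Add a derivation rule to Section 4.9.2 for each day up to Day 28:

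1. Assign level 7 from the date of death onward.
2. From discharge until readmission or the next contact, assign a prespecified not-hospitalized level, for example 2, updated at the Day 14 and Day 28 calls. Repeat with level 1 as a sensitivity analysis.
3. Summarise all ITT patients each day, by level and by mean change from baseline.

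The cost is a few sentences and a simple derivation. Discharge and death dates are already needed for the time-to-discharge and mortality analyses in Section 4.9.3, so no new data are collected. The downside is that level 1 versus 2 between contacts is assumed, not observed; the sensitivity analysis shows how much that matters.

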### 4.9.3 Secondary Efficacy Variables

Other secondary and exploratory endpoints will be analyzed according to the type of endpoint as described below. If data are sparse for any of the exploratory endpoints, summaries may be limited to descriptive statistics of available data or listings only as appropriate. By-patient listings of all secondary and exploratory efficacy endpoint data will be provided.

#### NEWS 2 scores

The NEWS is based on a simple aggregate scoring system (see Fig 2 for NEWS 2 scoring system) in which a score is allocated to physiological measurements, already recorded in routine practice, when patients present to, or are being monitored in hospital (**Error! Reference source not found.**). Six simple physiological parameters form the basis of the scoring system:

1. Respiration rate
2. Oxygen saturation
3. Systolic blood pressure
4. Pulse rate
5. Level of consciousness or new confusion\*
6. Temperature

\*The patient has new-onset confusion, disorientation and/or agitation, where previously their mental state was normal – this may be subtle. The patient may respond to questions coherently, but there is some confusion, disorientation and/or agitation. This would score 3 or 4 on the Glasgow Coma Scale (rather than the normal 5 for verbal response), and scores 3 on the NEWS system.

Standard descriptive statistics (mean, standard deviation, median, minimum, maximum) and change from baseline will be used to summarize each of these scores by treatment group and visit. NEWS scores will be assessed daily while patient is hospitalized. Plots of mean score (with standard error bars) by treatment group over time may be produced.

**Figure 2: The National Early Warning Score 2 (NEWS 2) scoring system**

Physiological parameter	Score						
	3	2	1	0	1	2	3
Respiration rate (per minute)	≤8		9–11	12–20		21–24	≥25
SpO 2 Scale 1 (%)	≤91	92–93	94–95	≥96			
SpO 2 Scale 2 (%)	≤83	84–85	86–87	88–92 ≥93 on air	93–94 on oxygen	95–96 on oxygen	≥97 on oxygen
Air or oxygen?		Oxygen		Air			
Systolic blood pressure (mmHg)	≤90	91–100	101–110	111–219			≥220
Pulse (per minute)	≤40		41–50	51–90	91–110	111–130	≥131
Consciousness				Alert			CVPU
Temperature (°C)	≤35.0		35.1–36.0	36.1–38.0	38.1–39.0	≥39.1	

### Mortality at Day 28

Incidence of mortality by Day 28 is the number of patients who have died by Day 28 and the percentage of patients reaching this endpoint will be summarized by treatment group. A CMH test will be used to test for a treatment effect of RESP301 + SOC versus SOC Alone after adjusting for baseline clinical status. Odds ratios of the treatment effect (RESP301 + SOC versus SOC Alone) with corresponding 95% confidence intervals (CI) will be estimated using a logistic regression model with baseline clinical status as a covariate. A treatment by baseline clinical status interaction may be added to the model along with other covariates of interest.

Overall survival will also be analyzed using time to event methods. Time to death is defined as the time from treatment start to death in days (*date of death – first dose date + 1*). Patients without a recorded death will be censored at their completion or at their early discontinuation date if they withdrew early or at their date of last assessment if they are alive and ongoing in study at time of analysis (*completion date/early discontinuation date/last assessment date – first dose date +1*). Reasons for censoring will be summarized.

The total number of patients with an event, the total number censored and Kaplan-Meier survival estimates with associated 95% CI (25th percentile, median, and 75% percentile, proportion surviving at Days 7, 10, 14, and 28) will be presented by treatment group. A survival plot will be produced with the probability of an event (0 to 100%) along the Y-axis and time in days along the X-axis.

The number of patients at risk will be presented along the X-axis. The hazard ratio of RESP301 + SOC versus SOC Alone with corresponding 95% CI and p-values will be estimated from a Cox Proportional model adjusting for treatment, and patients randomized strata.

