## 1 INTRODUCTION

Coronavirus disease 2019 (COVID-19) is a respiratory illness caused by a novel coronavirus (SARS-CoV-2). COVID-19 was first described in Wuhan, China, in December 2019 and is now a global pandemic (Matos et al, 2020). Most of those affected have milder illness (80%), 15% will be severely ill (require oxygen) and 5% will require intensive care unit care (Novel Coronavirus Pneumonia Emergency Response Epidemiology Team, 2020). Of those who are critically ill, most require early intubation and mechanical ventilation.

A critical early component of innate host defense in the airway is the ability of respiratory epithelial cells to produce high levels of NO (Kao et al, 2001). NO functions as a signaling molecule in initiation of the inflammatory response to viruses, and also has direct antiviral effects (Folkerts et al, 1998).

RESP301 is a NO-generating liquid designed to release NO in situ in the upper airways and deep in the alveolar spaces. RESP301 is delivered via a handheld nebulizer and has specific advantages over inhaled NO gas in treating patients with COVID-19 during the current pandemic.

This is an open-label, randomized, multicenter, parallel group, concurrent, controlled study using a sequential adaptive design. Participants will be consented and randomized 2:1 to the Investigational arm or the Control arm. Participants randomized to the Investigational arm will receive inhaled RESP301 (6 mL) administered using a nebulizer 3 times a day (TID) for up to 10 days in addition to the standard of care (SOC) while participants in the Control arm will receive SOC alone.

The analyses described in this SAP are based upon the following study documents:

- Study Protocol, Version 4.0 (September 16, 2020 )
- electronic Case Report Form (eCRF), Version 3.0 (June 24, 2020)
- RESP301 DMC Charter

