### 3 INVESTIGATIONAL PLAN

### 3.1 Overall Study Design and Plan

This is an open-label, randomized, multicenter, parallel group, concurrent, controlled study using a sequential adaptive design to evaluate the efficacy and safety of RESP301 added to standard of care (SOC) in hospitalized patients with COVID-19 (WHO ordinal scale grade 3 & 4).

Central stratified randomization of 300 subjects to assign participants into one of the study treatment arms will occur as follows, RESP301+SOC or SOC (control), with a randomization ratio of 2:1 using an interactive voice response system (IVRS)/interactive web response system (IWRS). Participants will be stratified by country and presence of risk factors for severe outcomes of COVID-19, based on comorbidities and age as follows:

1. Age  $>65$  years
2. Ongoing or currently treated diabetes mellitus
3. Ongoing or currently treated hypertension
4. Ongoing or currently treated cardiovascular disease
5. Ongoing or currently treated chronic lung disease
6. Cancer history of less than 3 years, basal cell skin carcinoma excluded
7. Ongoing or currently treated chronic kidney disease

Participants will be stratified as no risk factor (none of the above criteria), one risk factor (one single of the above) or high-risk factor (2 or more of the above).

There are 3 phases in the overall study design: Screening Period, Intervention Period, Follow-up Period. Figure 1 displays the study schematic.

**Screening Period**– Patients will be screened up to 2 days prior to treatment administration. Upon signing informed consent, the patient enters the screening phase and is assessed for the inclusion/exclusion criteria. If all eligibility criteria are met, the patient moves into the intervention period.

[figure not shown]
**Intervention Period** – The intervention period starts on Treatment Initiation (Day 1). Patients will receive treatment three times a day up to Day 10. Patients may end treatment earlier than Day 10 if their symptoms subside following the criteria outline in the protocol section 4.1.

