### 4.2 General Presentation Considerations

Baseline is the last available pre-treatment assessment. All assessments should have time collected. If time is not collected and date of assessment is the same as the *first dose date*, then assessment will be assumed to be collected prior to treatment unless schedule of assessments and protocol indicate planned collection is always after dosing.

Day-of-Discharge (DoD) is the day when patient is discharged from the hospital.

Durations are calculated as the stop date minus the start date plus one.

For elapsed time (e.g. time since the initial diagnosis), if the reference date is on or after the event date, then the elapsed time is the reference date minus the event date plus one. If the reference date is before the event date, then the elapsed time is the reference date minus the event date.

If more than one laboratory value is available for a given study day, the first valid observation will be used in summaries and all observations will be presented in listings. If it is not possible to determine which is the first measurement due to missing times, then the average of all measurements for that time point will be used as the value for that time point.

Continuous data will be summarized in terms of the mean, standard deviation (SD), median, minimum, maximum and number of observations, unless otherwise stated. Continuous data that are expected to be skewed will be presented in terms of the maximum, upper quartile, median, lower quartile, minimum and number of observations. The minimum and maximum will be reported to the same number of decimal places as the raw data recorded in the database. The mean, median, lower quartile and upper quartile will be reported to one more decimal place than the raw data recorded in the database. The SD will be reported to two more decimal places than the raw

---

data recorded in the database. In general, the maximum number of decimal places reported shall be four for any summary statistic.

The mixed model with repeated measurements /analysis of covariance model with treatment, country, participant's clinical status at Baseline and visit as the model term, and Baseline value as the covariate will be used to test for the significance of the treatment difference. Least square means, standard errors, 95% CIs and p-values will be presented.

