#### 4.7 Prior, Concomitant Medication and Prohibited Medication

Prior and concomitant medications will be summarized by drug class and preferred medication name by treatment group and for both treatment groups combined (Total) using the ITT population. Prior and concomitant medications will be summarized separately, concomitant medications will also be summarized overall and by study period. WHO DDE March 2020 will be used to classify medications.

Medication start and stop dates will be compared to the date of first dose of study drug to allow medications to be classified as either Prior only, both Prior and Concomitant, or Concomitant only. Missing or partial start dates will be imputed as described in [Section 4.9.1.3](#). Medications starting after the completion/withdrawal date will be listed but will not be classified or summarized.

Medications that start and stop prior to the date of first dose of study drug will be classified as Prior only. If a medication starts before the date of first dose of study drug and stops on or after the date of first dose of study drug, then the medication will be classified as both Prior and Concomitant. Medications will be classified as Concomitant only if they have a start date on or after the date of first dose of study drug.

Rescue medication of a ready-to-use nebulization of a bronchodilator will be allowed on study. The number and percentages of the patients using such medications will be summarized by treatment groups, and the impact on efficacy and safety will be analyzed by subgroup analyses.

By-patient listings of prior, concomitant and rescue medications will be provided. Listings will also be provided for any concomitant procedures reported.

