#### Time to hospital discharge survival

Time to hospital discharge is the time in the hospital after first study treatment in days (*date of discharge - first dose date + 1*). Patients who die before leaving the hospital will be considered failures (did not achieve hospital discharge), *date of death – first dose date +1* and censored. In the case that a patient is still hospitalized at time of analysis or withdraws from the study before leaving the hospital, they will be censored at their date of last assessment in the data cut or early discontinuation date, respectively.

The time to hospital discharge survival will be analyzed using Kaplan-Meier methods. If data allows, survival estimates will be stratified by baseline clinical status. The Cox models adjusting for baseline randomization strata may be performed.

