#### Time to Improvement

Time to improvement is the time in which the patient sees a decrease after first study treatment in the WHO 7-point ordinal scale from baseline to a value at least one level lower in days (*date of decrease in WHO scale - first dose date + 1*). In the case that a patient has not decreased in the WHO scale at time of analysis or withdraws from the study before leaving the hospital, they will

be censored at their date of last assessment in the data cut or early discontinuation date, respectively.

Time to improvement will be analyzed using the Kaplan-Meier methods as described in the above time to event analyses.

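### All four time-to-event endpoints are timed from the first dose date, which control patients and undosed RESP301 patients do not have

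*SAP*

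**What the plan says.** The SAP (version 2.0) fixes the time origin by formula in Section 4.9.3.

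- **Death:** "Time to death is defined as the time from treatment start to death in days". The formula subtracts the first dose date and adds 1, and censoring times are built the same way.
- **Discharge:** "Time to hospital discharge is the time in the hospital after first study treatment in days", with the same subtraction.
- **Improvement:** the time at which "the patient sees a decrease after first study treatment in the WHO 7-point ordinal scale", again counted from first dose.
- **Progression:** the mirror image of improvement, with the same origin.

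On who has such a date, Section 1 says that "participants in the Control arm will receive SOC alone". Section 4.5 puts all randomized patients in the efficacy analysis, and admits controls to the safety set because they were randomized to control, not because of a dose. Section 4.4.1 counts patients treated with any study drug separately from those randomized, so undosed RESP301 patients are foreseen.

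Three other rules lean on the same date.

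- **Baseline** (Section 4.2): "Baseline is the last available pre-treatment assessment". The fallback for untimed assessments ("If time is not collected and date of assessment is the same as the" first dose date) names the date outright.
- **Medications** (Section 4.7): "Medication start and stop dates will be compared to the date of first dose of study drug".
- **Partial start dates** of adverse events and medications (Section 4.9.1.3) are imputed against the first dose date.

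Two places use randomization instead. Section 3.1 times the second interim analysis at Day 14 after randomization. Section 4.9.1.3 censors overall survival at the randomization date when an imputed death date gives a negative time.

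**The concern.** A formula that subtracts a date which one arm never has cannot be computed for that arm. Taken literally, the Cox hazard ratio for death has no control group, and neither do the Kaplan-Meier comparisons of discharge, improvement and progression. Time to improvement and time to progression are key secondary endpoints in Section 3.3.1.

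A programmer will have to supply a date. One obvious patch is randomization for control and first dose for RESP301. The two arms then run on different clocks, undosed patients fall out of an analysis labelled intent-to-treat, and an event between randomization and first dose gets a time of zero or less. In an open-label trial, that choice should not be left until after the data are in view.

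**Working it through.** **1. How many patients have no start date.** Section 3.1 gives "Central stratified randomization of 300 subjects to assign participants into one of the study treatment arms" in a 2:1 ratio.

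- Final analysis: 300 × 1/3 = 100 control patients and 300 × 2/3 = 200 on RESP301. At least 100/300 = 33.3% have no first dose date.
- Second interim analysis: 50 of 150, the split stated in Section 4.9.1.5.
- If 2% to 5% of the RESP301 arm is never dosed (an assumption): 100 + 200 × 0.02 = 104, up to 100 + 200 × 0.05 = 110. That is 34.7% to 36.7% of 300.
- With the randomization date as origin, all 300 have a start date.

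**2. What the formula gives around randomization.** Time = event date − first dose date + 1.

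- Event one day before first dose: −1 + 1 = 0. Two days before: −2 + 1 = −1.
- Censoring at the randomization date, as Section 4.9.1.3 requires for some imputed deaths: 0 + 1 = 1 if dosed the same day, −1 + 1 = 0 if dosed one day later, −2 + 1 = −1 if two days later. The repair for a negative time can therefore itself give zero or a negative time.

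**3. Size of the bias if the arms get different origins.** The SAP has no figure to reproduce, so this is an illustration. Assumptions: no true effect; discharge times from a gamma distribution (shape 2.5, median 8 days) in both arms; times rounded up to whole days; follow-up cut at 28 days; control timed from randomization, RESP301 from a first dose *d* days later; hazard ratio from a Cox model.

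| Delay *d* | Spurious discharge hazard ratio (RESP301 vs control) |
|---|---|
| 0 (same day) | 1.00 |
| 0.5 day | about 1.07 |
| 1 day | 1.15 to 1.17 |
| 2 days | about 1.3 |

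The 2-day value depends on patients discharged before dosing. It is about 1.26 if they drop out and 1.32 to 1.33 if they are kept with the shortest possible time. With shape 2, medians of 6 to 10 days, pre-dose discharges dropped and a Mantel-Haenszel-type rate ratio, the figures are 1.09 to 1.14 for 1 day and 1.17 to 1.24 for 2 days. The direction is stable; the size depends on the model.

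**4. Direction by endpoint.** Shortening RESP301 times flatters it for discharge and improvement, where early is good. For death and progression, where early is bad, the shift tends to work against it.

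**5. What the delay can be.** The SAP does not give the interval from randomization to first dose. Section 3.1 allows up to 2 days from screening to treatment, and randomization falls inside that window. A note to Figure 1 allows screening and randomization on the same day, with Day 1 included in the screening period. So the delay can be nil, and 2 days is an outer bound.

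**The case against.** The strongest reply is that any competent team will use Day 1 for both arms. The protocol, or the addendum that Section 4.12 points to, may define Day 1 for controls, and if randomization and Day 1 coincide nothing is biased. The primary endpoint is a Day 14 proportion tested by a stratified Cochran-Mantel-Haenszel test and uses none of these formulas. The alpha plan in Section 4.9.1.4 covers only the interim and final looks, and no secondary endpoint is allotted confirmatory alpha. The discharge Cox model is one that may be performed, on an additional secondary endpoint.

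Most of this stands, and it limits the severity. It does not remove the error. Section 3.1 ties Day 1 to treatment initiation and does not say what that is for a patient on standard of care alone. The SAP prints its own formulas, and they would need correcting even if another document defines Day 1 for controls.

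Several stronger readings are tempting and not supported:

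- *That treatment-emergent status is set against first dose.* Section 4.10.1 uses the term without defining it. For adverse events, the first dose date enters through imputation of partial start dates.
- *That baseline is defined by the first dose date.* The definition says only pre-treatment; the date enters through the fallback for missing assessment times. The gap for controls is the same, but less explicit.
- *That the SAP allows a 2-day delay from randomization to dose.* The window runs from screening to treatment.
- *That the flaw generally favours RESP301.* It does for discharge and improvement, not for death and progression.

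**Conclusion.** The definitions are wrong as written. All four time-to-event endpoints use an origin that does not exist for about 100 of 300 randomized patients, or for any undosed RESP301 patient, and the SAP refers to randomization elsewhere. That conclusion follows from the text and needs no assumption about bias.

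The bias figures are conditional. They apply only if control is timed from randomization and RESP301 from a later dose, and they rest on an assumed delay and an assumed distribution of hospital stay. A delay of half a day to one day would distort the discharge hazard ratio by roughly 7% to 17%.

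A reader might infer that the primary result is compromised. The documents do not support that: the Day 14 proportion depends on this issue only through the baseline level and the day from which Day 14 is counted. The point should be fixed before analysis, but it does not threaten the primary test.

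**What to change.** - In Section 4.9.3, use the randomization date as time origin for death, discharge, improvement and progression in both arms, for event and censoring times alike.
- In Section 4.2, define baseline by one rule for both arms: the last assessment at or before randomization. Refer the rule for untimed assessments to the same date. A pre-dose allowance for RESP301 alone would bring the asymmetry back.
- In Sections 4.7 and 4.9.1.3, use the randomization date as reference for control and undosed patients.
- Keep the first dose date for exposure only.
- Reconcile this with Section 3.1, where Day 1 is treatment initiation and safety follow-up runs 28 days from first dose. State what Day 1, Day 14 and Day 28 are counted from in the control arm; do not simply equate randomization with Day 1.

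The cost is SAP wording and a change to the derivations. No new data should be needed: randomization details are already listed under Section 4.4.1, and the randomization date under Section 4.8.
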